### **Sample size analysis:**

Using our preliminary data, a sample size of 20 (10 per group) achieves 82.5% power to detect a difference in the knee flexion moment (KFM) impulse ILR of 0.283 during squats between the biofeedback (expected ILR=0.800±0.183) and standard of care group ( expected ILR=0.517±0.228) using a two-sided hypothesis test and p-value of 0.05. Group differences are based on our preliminary data after standard of care: KFM impulse ILR at 4 months (N=20): 0.517±0.228; KFM impulse ILR at 10 months (N=5): 0.971±0.183. Thus, our expected KFM impulse ILR for the biofeedback group at 3 and 6 months is 0.800±0.183. To test our hypothesis that the biofeedback group will walk with a greater KFM than the standard of care group, the minimal detectable change (MDC) of 0.09 N·m/kg·m with a standard deviation of 0.08 was used (Gardinier 2013). Using this expected group difference, a sample size of 28 (14 per group) achieves 81.7% power using a two-sized hypothesis test and p-value of 0.05. To account for 10% attrition, 32 participants will be enrolled.

A sample size of 30 (15 per group) achieves 81.0% power to detect a group difference of  $2.9 \pm 2.7$  milliseconds in T2 relaxation time (primary outcome; measured from 2 weeks to 6 months in the injured knee). This expected group difference is based on a change in T2 relaxation time of  $2.9 \pm 2.7$  milliseconds in the medial femoral cartilage by 6 months after ACLR as reported by Kumar et al. Preliminary data of 37 participants from our ongoing NIH R21 study indicate that quadriceps strength LSI following standard care is  $66.0 \pm 21.1\%$  at 6 months after ACLR. The evidence-based clinical targets for quadriceps strength at 6 months is 90.0%. Using the expected quadriceps strength LSI of 66.0% in the control group and 90.0% in the intervention group at 6 months after ACLR with a pooled standard deviation of 21.1%, a sample size of 30 (15 per group) achieves 91.8% power using a two-sided hypothesis. To account for attrition, 34 participants will be enrolled.

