**Sample Size and Randomization**

1. N=34 (17 in squat biofeedback group and 17 in control group)
  - a. Target equal number of women and men

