**Verbal Instructions For Control Group (completed on force plates; no mirror or any visual feedback):**

1. Complete squats keeping knees in line with toes
2. Keep hips back
3. Keep your weight evenly balanced between your feet

**Rest Breaks:** At least 30 seconds between each set

**Squat Depth:** 0-90° (as able)

**Arm Position:** Randomly varied by PT during each set (crossed over chest, straight out, or at side)

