## Statistical Analysis Plan

### **Data analysis plan:**

A p-value less than 0.05 will be considered statistically significant unless otherwise specified.

To determine the efficacy of the visual biofeedback program, analyses of covariance (ANCOVA) will be used at 3 and 6 months after ACLR to test differences in the interlimb ratio (ILR = injured limb / uninjured limb) of the knee flexion moment impulse during squatting, after adjusting for baseline knee flexion moment impulse. An ANCOVA will also be used to test differences in the ILR of the vertical ground reaction force impulse.

Independent t-tests will be used to test the percent change in cartilage T2 relaxation time in the injured knee from 2 weeks to 6 months after ACLR between groups, quadriceps strength, and gait biomechanics. For quadriceps strength, limb symmetry indexes will be computed (LSI = injured limb / uninjured limb x 100%).

If assumptions for any of these tests are violated, a nonparametric test will be conducted.

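### Does the 82.5% power for the squat knee flexion moment ratio fail at 6 months because its control value was measured at 4 months?

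*Combined protocol and SAP*

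**What the plan says.** The Data analysis plan states that "analyses of covariance (ANCOVA) will be used at 3 and 6 months after ACLR to test differences in the interlimb ratio" of KFM impulse during squatting, adjusted for baseline. Each visit therefore has its own test.

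The Sample size analysis covers this outcome once. A total of 20 patients "achieves 82.5% power to detect a difference in the knee flexion moment (KFM) impulse ILR of 0.283", taking 0.800±0.183 for biofeedback and 0.517±0.228 for standard of care. The source is then given: "Group differences are based on our preliminary data after standard of care", namely "KFM impulse ILR at 4 months (N=20): 0.517±0.228; KFM impulse ILR at 10 months (N=5): 0.971±0.183". From these the plan concludes that "our expected KFM impulse ILR for the biofeedback group at 3 and 6 months is 0.800±0.183". No visit is attached to the control arm's expected value where the power is stated.

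The same section labels T2 relaxation time as the primary outcome. The T2 and quadriceps calculations each use 15 per group, and after an allowance for attrition they lead to 34 patients. The section Sample Size and Randomization gives the same total: "N=34 (17 in squat biofeedback group and 17 in control group".

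**The concern.** The biofeedback arm has an expected ratio for 3 and 6 months. The control arm has a single value, measured at 4 months. That is close to the 3-month visit but two months short of the later one. The plan's own data suggest that the ratio rises under standard care, from 0.517 at 4 months to 0.971 at 10 months. If control patients have partly recovered by month 6 while biofeedback is held at 0.800, the true difference is below 0.283 and power falls.

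The plan does match the visit elsewhere. For quadriceps strength it writes "Using the expected quadriceps strength LSI of 66.0% in the control group and 90.0% in the intervention group at 6 months after ACLR", so the squat outcome looks like an oversight. A reader who took 82.5% to cover both visits might then read too much into a null 6-month result.

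**Working it through.** **Inputs (Sample size analysis).** Biofeedback 0.800, SD 0.183; control 0.517, SD 0.228; two-sided 0.05; 10 per group. Later standard-care mean 0.971, SD 0.183, N=5, at 10 months. Analysable numbers: 15 per arm (the basis of the T2 and quadriceps calculations) and 17 per arm (full enrolment).

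**1. The stated figure.**
- Common SD = √[(0.183² + 0.228²)/2] = 0.2067.
- Standardised difference = 0.283/0.2067 = 1.369.
- Noncentrality = 0.283/(0.2067 × √(2/10)) = 3.06 on 18 df. Noncentral t power = 82.5%, as stated.

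**2. Same inputs at the trial's size.** Power is 95.1% at 15 per arm and 97.2% at 17. The margin over the squat calculation arises because other outcomes set the sample size.

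**3. How far control may rise before power drops below 80%, with biofeedback at 0.800.** The share is the rise from 0.517 divided by 0.971 − 0.517 = 0.454. The ANCOVA rows assume a baseline correlation of 0.5 (the documents give none), so the SD is 0.2067 × √(1 − 0.5²) = 0.179, on 2n − 3 df.

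| Test | n per arm | Difference for 80% | Highest control ratio | Rise from 0.517 | Share of 0.454 |
|---|---|---|---|---|---|
| Unadjusted t | 15 | 0.219 | 0.581 | 0.064 | 14% |
| Unadjusted t | 17 | 0.205 | 0.595 | 0.078 | 17% |
| ANCOVA, r = 0.5 | 15 | 0.190 | 0.610 | 0.093 | 20% |
| ANCOVA, r = 0.5 | 17 | 0.178 | 0.622 | 0.105 | 23% |

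**4. One illustration: straight-line recovery from month 4 to month 10.**
- Control at 6 months = 0.517 + 0.454 × 2/6 = 0.668, so the difference is 0.132.
- Unadjusted power: 39% (15 per arm), 44% (17 per arm).
- ANCOVA, assumed r = 0.5: 49%, 55%. Assumed r = 0.7: 65%, 71%.

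**5. How firm the illustration is.**
- The 10-month mean has standard error 0.183/√5 = 0.082. With t = 2.776 on 4 df, its 95% interval is 0.971 ± 0.227, or 0.74 to 1.20.
- The standard error of the 6-month interpolation is √[(4/6 × 0.0510)² + (2/6 × 0.0818)²] = 0.0436, where 0.0510 = 0.228/√20. This gives about 0.576 to 0.760 on 17.3 df, if the two samples are independent, which the documents do not say.
- Unadjusted power across that interval runs from 82% (15 per arm) or 86% (17 per arm) at the low end to about 8% at the high end.
- The interval leaves out 0.517 only because a straight line has been imposed. Recovery that comes mostly after month 6 would be compatible with 0.517.

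Across the control values considered, from 0.517 to 0.760, unadjusted 6-month power runs from about 97% down to 8%. The documents do not narrow that range.

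**The case for a change.** The strongest case for a change is that the efficacy of the programme is judged by this analysis at both visits, that the plan's own later value points upward, and that the tolerance is small: an unadjusted rise of 0.064 to 0.078 uses it up. The larger sample and the baseline adjustment help, but in the straight-line scenario neither restores 80%. One or two sentences in the plan would put the assumption on record, with no extra patients and no new test.

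Much of this stands. Nothing in the plan justifies carrying 0.517 to month 6, and a sentence saying so would be harmless. But the natural reading is that one contrast, 0.800 against 0.517, was meant for both visits, so a 6-month control assumption exists, though without support. The plan already discloses that 0.517 comes from month 4 and that the 10-month mean comes from five patients, so a careful reader can see the limitation. No 6-month control value is available in the documents, so any added power statement would be a range too wide to guide anyone. A null 6-month result would in any case be judged by its estimate and confidence interval.

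**Conclusion.** No change is needed. The 82.5% is arithmetically right for its stated inputs and serves reasonably for the 3-month comparison. At 6 months it depends on a control ratio near 0.517, which the plan neither defends nor contradicts with data from that visit. With biofeedback at 0.800 and the plan's SDs, 15 to 17 per arm keep unadjusted power at 80% or more up to a control ratio of about 0.58 to 0.60, or about 0.61 to 0.62 under ANCOVA with an assumed correlation of 0.5. The 39% to 44% figure rests on assumed linear recovery towards a mean from five patients and cannot be presented as the trial's power.

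Writing the assumption down would leave the test, the T2 primary outcome and N=34 as they are, because the squat calculation needs only 20 patients and does not drive enrolment. This is a missing justification for an outcome that does not set the sample size. The report can deal with it by giving the 6-month difference with its confidence interval.

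### The 91.8% power stated for quadriceps strength is not the two-sided figure: the plan's own inputs give 85.2% at two-sided 0.05

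*Combined protocol and SAP*

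**What the plan says.** The sample size analysis in the SAP gives four power statements. The one for quadriceps strength is based on the "expected quadriceps strength LSI of 66.0% in the control group and 90.0% in the intervention group at 6 months after ACLR". The spread is taken as 21.1% (pooled), and the conclusion drawn is that "a sample size of 30 (15 per group) achieves 91.8% power using a two-sided hypothesis". Unlike the two knee flexion moment statements in the same section, it gives no significance level of its own.

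The data analysis plan supplies the level: "A p-value less than 0.05 will be considered statistically significant unless otherwise specified". It also supplies the test. The sentence that begins "Independent t-tests will be used to test the percent change in cartilage T2 relaxation time in the injured knee" goes on to list quadriceps strength among the outcomes to be compared in this way.

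The section ends: "To account for attrition, 34 participants will be enrolled".

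**The concern.** Mean difference, standard deviation, group size, test, sidedness and default significance level are all in the documents, so the power can be recalculated without any outside figure. The standardised difference is 24.0/21.1 = 1.137. For a two-sided 0.05 t-test with 15 per group, 91.8% is too high for an effect of that size.

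Two things are at stake. First, a reader who meets a null strength result would take the chance of a false negative under the assumed effect to be about 8%, when the planned test gives almost 15%. Second, a number that matches a one-sided test beside text that says two-sided leaves some doubt about which test will be applied to strength. A one-sided test at 0.05 would be an easier bar to clear.

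**Working it through.** **Inputs**

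| Quantity | Value | Source |
|---|---|---|
| Means | 66.0% control, 90.0% intervention | SAP, sample size analysis |
| Difference | 90.0 − 66.0 = 24.0 points | arithmetic |
| Pooled SD | 21.1% | SAP, sample size analysis |
| Group size | 15 per group | SAP, sample size analysis |
| Sidedness | two-sided | SAP, sample size analysis |
| Alpha | 0.05 (default) | SAP, data analysis plan |
| Test | independent two-sample t-test | SAP, data analysis plan |

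**Formula.** With n per group, the t statistic has df = 2n − 2 and noncentrality δ = difference / (SD × √(2/n)). Two-sided power is P(|T| > c), where T is noncentral t with that df and δ, and c is the 1 − alpha/2 quantile of central t. One-sided power is P(T > c) with c the 1 − alpha quantile.

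**Numbers.** df = 28 and δ = 24/(21.1 × √(2/15)) = 3.115.

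**Attempt to reproduce the plan's 91.8% at 15 per group**

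| Calculation | Critical value | Power |
|---|---|---|
| Two-sided 0.05, t-test (as the text states) | 2.048 | **85.2%** |
| Two-sided 0.05, normal approximation | 1.960 | 87.6% |
| One-sided 0.05, t-test | 1.701 | **91.8%** |
| Two-sided 0.10, t-test | 1.701 | 91.8% |

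The stated figure does not reproduce two-sided at 0.05 by either method. It matches one-sided 0.05 to the printed decimal. A two-sided 0.10 test has the same critical value and so the same power, but no such level appears in the documents.

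**Rounding of the inputs.** Each mean could be off by 0.05 and the SD by 0.05. The extremes are a difference of 23.9 with SD 21.15 (84.8%) and a difference of 24.1 with SD 21.05 (85.7%). Rounding does not explain the gap.

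**What 91.8% would require.** At 15 per group and two-sided 0.05, it needs an SD of about 18.9 or a difference of about 26.8 points. With the stated difference and SD, power is 89.5% at 17 per group (full enrolment with no loss), 91.2% at 18 and 92.7% at 19.

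**The same method on the plan's other three figures**

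| Outcome | Inputs | Stated | Two-sided 0.05 | One-sided 0.05 |
|---|---|---|---|---|
| Squat knee flexion moment impulse ratio | 0.283; SDs 0.183 and 0.228 (pooled √((0.183² + 0.228²)/2) = 0.207); 10 per group | 82.5% | 82.5% | 90.3% |
| Walking knee flexion moment | 0.09; SD 0.08; 14 per group | 81.7% | 81.7% | 89.5% |
| T2 relaxation time | 2.9; SD 2.7; 15 per group | 81.0% | 81.0% | 89.0% |

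All three agree with the two-sided calculation to the printed decimal and none with the one-sided. A general difference in software or method is therefore not the explanation.

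**Size of the error.** 91.8 − 85.2 = 6.6 percentage points. Type II error is 100 − 85.2 = 14.8%, against the implied 100 − 91.8 = 8.2%, a ratio of 14.8/8.2 = 1.8.

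**The case against.** The strongest case on the other side is that nothing depends on this number. T2 relaxation time carries the primary label and needs 15 per group at 81.0%, so the enrolment of 34 would stand if the strength sentence were deleted. The plan never sets a 90% target for strength, and the corrected 85.2% is still higher than the power quoted for the other three outcomes. All of that is right. It limits the consequences to the accuracy of the statement; it does not make the statement correct.

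A second objection is that the cause is inferred. The sentence gives no alpha, and a two-sided 0.10 test fits 91.8% as well as a one-sided 0.05 test does. This also stands as far as it goes: the documents do not show how the calculation was run. But the data analysis plan sets 0.05 unless otherwise specified, nothing else is specified for strength, and 0.10 appears nowhere. If another level or a one-sided test was intended, the sentence is still wrong, because it omits the level or misstates the sidedness.

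**Conclusion.** The concern holds. Under the test the plan specifies, power for quadriceps strength with 15 per group is 85.2%, not 91.8%. The overstatement is 6.6 points, and the chance of missing the assumed effect is about 1.8 times what the plan implies. This rests on the stated means, SD and group size, on the independent t-test, and on the 0.05 default applying to a sentence that gives no level. That 91.8% does not follow from those inputs is arithmetic. That it came from a one-sided run is the likeliest explanation, given the exact match, but it is not proved. The practical effect is modest: power remains above 80% and neither the sample size nor the analysis changes.

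**What to change.** In the quadriceps strength sentence of the sample size analysis, replace 91.8% with 85.2% and add that this is for a two-sided test at alpha 0.05, as the two knee flexion moment statements already do. The plan could also report 89.5% for 17 per group, the power if all 34 enrolled participants are analysed. If a one-sided test or a different level was in fact intended for strength, the sample size analysis and the data analysis plan should both say so and justify it before the data are analysed.

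The cost is one number and a short phrase. The stated power becomes slightly less favourable; enrolment, procedures and the planned tests stay as they are.
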